For testing the null-hypothesis of no difference between the risk scores regarding the proportion of individuals selected for screening, McNemar's Test will be used.

Description of the primary analysis and population:

The primary analysis will be conducted of all volunteers within the overall study population after 2 LDCT screening rounds.

5.1.2 Secondary Objective(s): Calculation of Epidemiological Measure(s) of Interest (e.g. hazard ratios, incidence rates, test/retest reliability)

1. Rate/rate ratio of initiation of cardiovascular treatments (in particular lipid-lowering) in the calcium score reporting group vs. the non-reporting group after year 1 of study:

2. Efficiency of nodule management algorithms:

Based on the two alternative management algorithms (LungRads1.1 alone or LungRads1.1 + PanCan) patients are sorted into three management groups: (a) next surveillance scan, (b) early recall scan, or (c) diagnostic evaluation recommended. For one algorithm to be more efficient, the following criteria must both be fulfilled

- i. The number of patients without cancer sorted in the category (a) is higher AND
- ii. The number of patients with lung cancer sorted into category (b) or (c) is higher.

3. Success of screening program. Based on all individuals enrolled. Definition of success is calculated using:

a. Response rate (number of responses/overall number contacted), number of drop-outs, effectiveness of patient recruitment via mailings vs. GPs referrals (individual response rates)

b. Percentage of subjects meeting all inclusion/exclusion criteria

c. Repeatability of the PLCO score

d. Percentage of subjects receiving an adequate low-dose CT scan according to DRG guidelines (number of diagnostic CTs/number of all CTs)

4. Quality of screening program.

a. CT reading performance (2nd reader vs. CAD vs. AI)

b. Frequency of detection and management of incidental findings from low dose chest CT (emphysema, coronary heart disease, etc.)

c. Subsequent identification of biomarkers with predictive value / correlation with positive LDCT findings / cancer risk

5. Smoking cessation

a. Success of smoking cessation counseling based on number of participants quitting with or without revealing additional health risks (emphysema score, coronary calcium score or both).

6. Blood-based and exhalation- based biomarkers

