For the HANSE study the calibrated threshold for the PLCO 5 year risk score of 1,314% was converted to a 6year threshold of 1,58% , because the original PLCO risk score calculates the 6year risk and thus the original calculators by Tammemägi et al. can be used for the HANSE study (13).For this conversion linearity between year 5 and 6 was assumed.

(ii) Sample size for the evaluation of **initiation of cardiovascular therapy** within 1 year after randomization has been calculated using Chi-Square Test and two-sided type-I-error rate of 5% based on the results of the ITALUNG study (15,16), where for 44% of all patients coronary artery calcification (CAC) was detected. In the ITALUNG study, 63% of patients with CAC were on cardiovascular treatment without receiving results of their low dose CT screening. For this study, where the patients are randomized to either reporting or non-reporting of CT screening results, we conservatively assume that the non-reporting group shows a rate of cardiovascular treatment of 68%. In contrast, as an effect of reporting the screening results, we assume that in the reporting group 73% of patients receive cardiovascular treatment, so the effect of reporting the CT results is assumed to be an increase of 5 percentage points in the cardiovascular treatment rate. Acknowledging that only 44% of all patients are assumed to show CAC on low dose CT, the expected difference between the reporting and non-reporting group is $(73\% - 68\%) * 44\% = 2.2\%$. Equivalently, the assumed rate ratio between the reporting and non-reporting group is $(73\% * 44\%) / (68\% * 44\%) = 1.07$. With 2,500 patients randomized to each arm and using a Chi-Square Test with a two-sided type-I-error rate of 5% for testing the null-hypothesis of no difference between the groups, the statistical power is 97%.

(iii) To evaluate the power of potential **longitudinal follow-up** studies based on this screening trial, the power for the 10 year mortality endpoint has been calculated based on the results of the NELSON study using a Chi-Square Test with a two-sided type-I-error rate of 5% for testing the null-hypothesis of no difference in 10-year cardiovascular mortality rates between the

reporting and non-reporting groups. In line with the results of the NELSON study, we assume a 10 year cardiovascular mortality rate in the non-reporting group of 2.7%.

[figure not shown]

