- Non-qualifying subjects (who did not meet the NELSON inclusion criteria or PLCO criteria) will be asked to volunteer by contributing long-term outcome data informing of the development of lung cancer or death from lung cancer. In addition NELSON and PLCO non-qualified subjects with a smoking history, who volunteered to participate in the HANSE study, will be contacted via mail after 5 years to inquire if they developed lung cancer in the time between their recruitment and present. Non-responders will be followed by local cancer registries and by phone.

2. **LDCT - 1. Screening round**

- **Lung function test:** All included participants will receive a lung function test prior to undergoing LDCT.
- **Cardiovascular health:** All participants will be questioned whether they receive treatment for any cardiovascular conditions. Blood pressure, heart rate and BMI data (height and weight) will be obtained.
- Assessment of current **COPD treatment medication.**
- **Randomization:** Subjects included in the screening study will be randomized prior to receiving the initial LDCT scan. Randomization will not affect the procedure and the schedule of the cancer screening process but only determine the allocation of the participants of the coronary calcium score and emphysema score to the reporting and the non-reporting group. Randomization ratio of 1:1 and a 2-factorial design ($\frac{1}{4}$ calcium score only; $\frac{1}{4}$ emphysema score only, $\frac{1}{4}$ both; $\frac{1}{4}$ none) will provide equally sized groups of patients in both groups including age (5 year groups) and sex stratification .

Lung LDCT assessment:

- **Standardized and quality-assured image analysis** will be conducted using state-of-the-art artificial intelligence (AI)-based detection and nodule measurement software (Coreline) to support the radiologist. CT assessment of lung nodules will be performed according to LungRADS 1.1 criteria (see Appendix), as well as volume doubling time according to the European position statement on lung cancer screening (14).
- Inspection of **lungs for nodules** will be carried out for all subjects, independent of the assigned groups (reporting or non-reporting).
- An independent 2nd read by an additional radiologist using the same reading software algorithm will be performed.
- Subjects with no nodules or those of LungRADS grades 1, 2, 3, 4a will be scheduled for follow-up scans at intervals according to LungRADS schedule (see Appendix).

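### The only test named for the cardiovascular-treatment comparison ignores the randomisation strata and baseline treatment: a small loss from age and sex, a possibly larger one from baseline treatment

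*Protocol*

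**What the plan says.** - **Allocation.** Protocol section 6.1.2 (Randomization) sets "Randomization ratio of 1:1 and a 2-factorial design" for calcium score and emphysema score reporting, "including age (5 year groups) and sex stratification". Section 5.2.1 repeats the age and sex stratification.
- **Baseline data.** At the first screening round, section 6.1.2 says: "All participants will be questioned whether they receive treatment for any cardiovascular conditions". At the 1-year round, participants are asked whether they started such treatment during the study.
- **Analysis section.** Section 5.1.2, item 1, lists "Rate/rate ratio of initiation of cardiovascular treatments (in particular lipid-lowering) in the calcium score reporting group vs. the non-reporting group" after year 1. It names no test, model, strata or covariates.
- **Sample size section.** Section 5.3 (ii), with matching text in the synopsis, computes power "using a Chi-Square Test with a two-sided type-I-error rate of 5% for testing the null-hypothesis of no difference between the groups", with 2,500 per arm. It assumes 68% treated without reporting and 73% with reporting. It then says that only 44% of participants are expected to have coronary calcification, so that the expected difference is 2.2 points, and states 97% power.
- **Status.** Sections 2.2 and 4.2 make this a secondary matter (the main secondary objective). Section 5.2.2 declares all secondary parameters exploratory.

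**The concern.** Stratified allocation balances the arms on age and sex. If age and sex predict cardiovascular treatment, the true variance of the difference between arms is smaller than an unstratified chi-square assumes. The test then uses too large a standard error, rejects less often than 5% under the null, and loses some power.

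Baseline cardiovascular treatment is not a stratification factor, so omitting it makes no standard error wrong. But it is likely to be the best single predictor of treatment a year later, it is already collected, and the one stated method makes no use of it.

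At stake is the precision of the comparison behind the main secondary objective, where the protocol itself expects a difference of only 2.2 points across all randomised participants.

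**Working it through.** **Inputs from section 5.3 (ii):** 2,500 per arm, two-sided 5%, 68% and 73% treated, 44% with calcification. **Not in the protocol, so assumed:** the share of outcome variance explained by age and sex (R² of 1 to 10%), and the correlation r between baseline and 1-year treatment (0.6 to 0.8).

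**1. The stated power.** At 68% against 73% the pooled proportion is 0.705.
SE = √(0.705 × 0.295 × 2/2500) = 0.0129; z = 0.05/0.0129 = 3.88; power = Φ(3.88 − 1.96) = 97%.
The stated figure is reproduced, but only with the full 5-point difference applied to all 2,500 per arm.

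**2. The same test at the 2.2-point difference.** The rates are 0.44 × 68% = 29.92% and 0.44 × 73% = 32.12%.
SE = √(0.2992 × 0.7008/2500 + 0.3212 × 0.6788/2500) = 0.0131; z = 0.022/0.0131 = 1.68; power = Φ(1.68 − 1.96) = 39%.
These rates count nobody without calcification as treated. If 20 to 68% of them are treated equally in both arms, power is 34 to 39%.

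**3. Age and sex.** Adjustment multiplies the SE by √(1 − R²). The last column is the type I error of the unadjusted test with balanced strata, 2 × [1 − Φ(1.96/√(1 − R²))].

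| R² | SE factor | Power, 2.2 points | Power, 68% vs 73% | Unadjusted type I error |
|---|---|---|---|---|
| 0 | 1.000 | 39.0% | 97.2% | 5.0% |
| 1% | 0.995 | 39.4% | 97.4% | 4.9% |
| 5% | 0.975 | 40.7% | 97.8% | 4.4% |
| 10% | 0.949 | 42.6% | 98.3% | 3.9% |

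A simulation agrees (10 equal age-by-sex strata, exact balance, 20,000 runs per setting, chi-square against Cochran-Mantel-Haenszel):
- R² about 3.5%: power 38.7% against 40.0% at 2.2 points, and 97.4% against 97.7% at 68% vs 73%. Chi-square type I error 4.6 to 4.7%.
- R² about 8%: power 38.5% against 41.7%, and 97.7% against 98.2%. Chi-square type I error 4.0 to 4.2%.

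The stratified test held 4.9 to 5.1% in these settings.

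**4. Baseline treatment, if the outcome is being on treatment at 1 year.** The SE factor is √(1 − r²), applied to z = 1.68 from step 2.
- r = 0.6: factor 0.80, z = 2.10, power 56%.
- r = 0.7: factor 0.71, z = 2.36, power 65%.
- r = 0.8: factor 0.60, z = 2.80, power 80%.

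As an illustration of plausibility, section 5.3 (ii) cites 63% of patients with calcification on treatment without their CT result. Reading 63% as the baseline rate, 68% as the 1-year rate, and assuming that nobody stops, r = (0.63 − 0.63 × 0.68)/√(0.63 × 0.37 × 0.68 × 0.32) = 0.90 in that subgroup. Stopping would lower it.

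**5. If the outcome is new initiation.** Step 4 does not carry over. Someone already treated may be unable to start the same treatment, so baseline status mainly determines who is at risk. The protocol names initiation as the endpoint (sections 4.2 and 5.1.2), yet its 68% and 73% are rates of receiving treatment.

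**The case against.** The strongest reply is that the chi-square is a sizing device. It stands only in the power calculation. Section 5.1.2 fixes no test, section 6.1.2 says only that the groups will be compared, and a statistical analysis plan that is not at hand may specify an adjusted model. This stands in part: the protocol cannot be said to commit its final analysis to a chi-square. But that remains the only method it states for this comparison.

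Second, the loss from ignoring age and sex is small and errs on the safe side. This stands. At the protocol's own 68% against 73%, there is almost nothing to gain.

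Third, the large gain comes from a factor outside the stratification, from correlations that the protocol does not give, and from one of two possible readings of the outcome. This stands too, and the gain must be presented as conditional.

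Fourth, the endpoint is exploratory, so no confirmatory conclusion depends on it. This stands and limits the weight of the point.

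**Conclusion.** The point holds as a low-cost improvement, not as an error that invalidates the comparison. For age and sex, over an assumed R² of 1 to 10%, the SE is up to about 5% too large and the power loss is about 0 to 4 points at the 2.2-point difference. For baseline treatment, the possible gain is from 39% to about 56 to 80%. That assumes a correlation of 0.6 to 0.8 and an outcome of being on treatment; it is less for strictly new initiation.

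A reader might infer more than this, but the protocol does not support it:
- *That the test is invalid or inflates false positives.* Ignoring the strata makes it conservative, and omitting baseline treatment costs precision only.
- *That baseline treatment is collected and goes unused.* It may well serve to establish who newly started treatment.
- *That missing adjustment explains the 39%.* That figure arises because the stated 97% does not apply the 44% dilution given in the same paragraph. This is a separate issue; adjustment for age and sex recovers at most about 4 of the 58 points between 97% and 39%.
- *That a confirmatory result is at risk.* Section 5.2.2 makes the endpoint exploratory.

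**What to change.** In section 5.1.2, item 1, state that the reporting against non-reporting comparison is estimated with stratification or adjustment for 5-year age group, sex, the other reporting factor (emphysema score) and baseline cardiovascular treatment. Either a Mantel-Haenszel risk difference or ratio, or a regression model giving a marginal risk difference or ratio, would serve and would match the rate ratio already listed there. Keep the unadjusted result as supportive.

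State in the same place whether the outcome is being on treatment at 1 year or newly starting it. If it is newly starting, use baseline treatment to define who can initiate, and not simply as a covariate.

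The cost is a sentence or two. All the variables are already collected, and ages 55 to 79 in 5-year groups by sex give 10 strata, on average 5,000/10 = 500 participants each, so sparse strata should not be a difficulty. The 97% power statement needs its own correction.

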4.2 Outcomes

Primary endpoints:

1. Proportion of lung cancers detected with different risk models

To address the suitability of different inclusion methods for identifying the high-risk population for screening, the PLCO_M2012 model and the NELSON inclusion criteria will be compared primarily for the positive predictive value of lung cancers detected within the study population after 2 screening rounds.

Key-Secondary endpoints:

Additionally, the PLCO_M2012 model and the NELSON inclusion criteria will be compared in a hierarchical order regarding the key secondary endpoints:

1. Proportion of individuals selected for screening within the high-risk study population
2. Proportion of lung cancers detected with different inclusion methods (NELSON vs. PLCO) within the overall study population after 5 years
3. Proportion of lung cancers detected within the high-risk population
4. Sensitivity within the overall population after 5 years.

5. Specificity within the overall population after 5 years.

Secondary endpoints:

6. **Rate of initiation of cardiovascular treatments** (in particular lipid-lowering) in the calcium score reporting group vs. the non-reporting group after year 1 of study.
7. **Efficiency of nodule management algorithms:** Based on the two alternative management algorithms (LungRads1.1 alone or LungRads1.1 + PanCan/AI) participants are sorted into three management groups: (a) next surveillance scan, (b) early recall scan, or (c) diagnostic evaluation recommended. For one algorithm to be more efficient, the following criteria must both be fulfilled
 - i. The number of participants without cancer sorted in the category (a) is higher AND
 - ii. The number of participants with lung cancer sorted into category (b) or (c) is higher.
8. **Success of screening program.** Based on all individuals enrolled. Definition of success is calculated using:
 - a. Response rate (1. Respondents to questionnaire / invitation: those who send their smoking history & other relevant data; 2. among the above respondents, those who are eligible by one of the two criteria, or both; 3. those who are eligible, and actually take part in the screening), number of drop-outs, effectiveness of patient recruitment via mailings vs. GPs referrals (individual response rates)
 - b. Reliability of PLCO risk scoring (self-reported vs. on site assessment)

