- Findings categorized as LungRADS Cat. 4b or 4X nodules will be presented to the local Multidisciplinary Tumor Board (MDT) for further assessment and treatment decisions in the clinical routine workflow.
- **Emphysema** severity as a measure for tobacco related lung destruction will be quantitatively assessed on the LDCT images using the fully automated artificial intelligence (AI)-based algorithm of the Coreline software (Coreline, Seoul South Korea). The data will either be reported to study participants and treating physicians or not according to the allocation of the individual to the two randomized experimental groups.
- **Coronary calcium scores** (Agatston score) will be assessed using the fully automated artificial intelligence (AI)-based algorithm of the Coreline software (Coreline, Seoul South Korea). However, only the reporting group will receive the results of the score, together with an explanation of potential consequences of these findings for their cardiovascular health and with recommendation to seek specific consultation with their general practitioner or specialist. In this group a report is sent to the participants' GP.
- The LDCT image data, the coronary calcium score and % emphysema of the non-reporting group will remain confidential and will be stored for further assessment at year 1 (follow-up CT screen) and for evaluation of endpoints at year 5 and 10 (not part of this funding period).
- Apart from the randomized reporting of coronary artery calcium score and % emphysema **clinically relevant incidental findings** will be categorized in emergent (within 1-30 days), timely (within 1-6 months) or regular (>6 months) follow up. They will always be included in the CT report for the study participants.

- For emergent findings the study participant will be contacted directly by the local study team.
- Clinically non-relevant CT findings (i.e. liver or kidney cysts) not requiring physician consultation will not be included in the report.

Smoking cessation program:

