smoking cessation program. A team of clinical and health economic experts will define the detailed structure of the model.

- **Outcome analyses:** For each screening scenario, a Monte Carlo simulation (MCS) with 1,000 iterations will be performed to estimate expected outcomes and MSC-based confidence intervals. Primary outcomes of the analysis are long-term all-cause mortality, additional costs per quality-adjusted life year (QALY) gained, per life year (LY) gained or per death averted. Efficiency frontiers will be constructed for each primary outcome to identify efficient screening scenarios and calculate the incremental cost-effectiveness of these scenarios. The impact of variations in the values of key input parameters (adherence to screening, smoking cessation etc.) on model outcomes will be tested in sensitivity analyses.

Consequences of screening:

- All screened individuals will ask to participate in a 'Consequences of Screening' survey in order to evaluate their emotional and psychological condition during the screening process. Survey will be based on the psychological consequences questionnaire, adapted for lung cancer screening (19).
- In addition, the patient questionnaire will evaluate the socioeconomic background, smoking cessation, lung and cardiovascular health.
- The exact questions of the questionnaire will be determined before the study start and included in the appendix of the protocol.
- GP contact information is recorded.
- Current medication is recorded.

3. LDCT 1 year - 2. Screening round

Timing of the follow-up chest CT according to LungRADS 1.1 schedule.

Chest LDCT scan procedure and image analysis as in the 1st screening round.

- **Lung LDCT assessment:** Assessment of newly identified lung nodules will be done according to LungRADS 1.1 criteria. Follow-up radiographic assessment of solid nodules will be based upon volume doubling time (VDT) as a key driver for recommendations on further course of action.
- **Lung function test:** All included participants will receive a lung function test prior to undergoing LDCT.

- **Cardiovascular health:** All participants will be questioned whether they initiated treatment for any cardiovascular conditions during the study. Blood pressure, heart rate, and BMI data will be obtained.
- Additionally, the study is designed to analyze cardiovascular events and mortality in a follow-up study at year 5 and 10 (not part of the current funding period).

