- **Assessment of smoking status:** Success of the smoking cessation program will be evaluated using a questionnaire, combined with a urine cotinine check (in quitters).
- **Initiation of COPD treatment:** Assessment of COPD treatment initiation during the study.
- **Consequences of screening:** Questionnaire 'Consequences of Screening' as above.

2. Evaluation

Lung cancer screening:

- The percentage of subjects receiving an adequate low-dose CT scan according to DRG guidelines will be assessed.
- For all included participants, detection rate of lung cancers will be evaluated and categorized according to LungRADS 1.1 categories.
- Detected (proven by histopathology) lung cancers will be categorized whether they were predicted by PLCO or NELSON or both. Statistical analysis will reveal potential advantages of either risk scoring methodology.
- A retrospective analysis will compare this algorithm to the PanCan nodule algorithm vs. AI for management efficiency. Based on the two alternative management algorithms patients are sorted into three management groups: (a) next surveillance scan, (b) early recall scan, or (c) diagnostic evaluation recommended. For one algorithm to be more efficient, the following criteria must both be fulfilled
 - The number of patients without lung cancer sorted in the category (a) is higher AND
 - The number of patients with lung cancer sorted into category (b) or (c) is higher.

Coronary calcium score / cardio-vascular treatment initiation:

- At the 1-year follow-up visit, the rate of initiation of cardiovascular treatment (in particular lipid-lowering) will be determined, together with BMI, and blood pressure data. Data for the calcium score reporting group will be compared to those of the non-reporting group.

Smoking cessation:

- Success of smoking cessation counseling will be based on the number of participants quitting (% quitters) within study period.
- Allocation of the participants to the different experimental groups will allow determining the influence of 'reporting' of prognostic markers (percent emphysema and coronary calcium score) on smoking cessation.

All methods will be performed according to study site SOPs.

CT analysis software (Coreline) specifications:

1. Viewer function

- LCS (Lung Cancer Screening) viewer functions

- Image display with axial, sagittal and coronal images and 3D rendering.
- Virtual slice thickness control display function for MPR (Multi-Planar Reformat) images.

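### Year-1 initiation of cardiovascular treatment rests on a broad question to participants who know their allocation; a repeat of the baseline medication list would be a sounder source

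*Protocol*

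**What the plan says.** Protocol Section 4.2 (secondary endpoint 6) defines the outcome as the rate of starting cardiovascular treatments, "in particular lipid-lowering) in the calcium score reporting group vs. the non-reporting group after year 1 of study". Section 2.2 names this as the main secondary objective. Section 5.2.2 makes all secondary parameters exploratory.

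Section 6.1.2 describes how the data are obtained:

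- **Round 1, cardiovascular item:** "All participants will be questioned whether they receive treatment for any cardiovascular conditions".
- **Round 1, medication:** qualified staff assess current medication on site during recruitment. The list under the sub-heading on consequences of screening adds "Current medication is recorded".
- **Round 2, cardiovascular item:** "All participants will be questioned whether they initiated treatment for any cardiovascular conditions during the study". No medication list appears among the year-1 items.
- **Evaluation:** at the 1-year visit "the rate of initiation of cardiovascular treatment (in particular lipid-lowering) will be determined, together with BMI, and blood pressure data". No source other than the question is named.
- **Openness:** "only the reporting group will receive the results of the score, together with an explanation of potential consequences" and advice to consult a doctor, and a report goes to the GP in that group.

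Section 5.3 (ii) plans the comparison with 2,500 per arm and a two-sided 5% chi-square test. It cites an earlier screening trial in which "63% of patients with CAC were on cardiovascular treatment without receiving results of their low dose CT screening".

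**The concern.** Two problems follow from the stated method.

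**Reporting that differs by arm.** One group has been given a score, told what it may mean and advised to see a doctor. A year later both groups are asked whether they started treatment. Recall, or the wish to report having followed the advice, can differ between arms even if prescribing does not. No record check or blinded classification is stated for this outcome. Elsewhere the protocol does verify: urine cotinine in self-declared quitters, and hospital or registry documents for cancers in the low-risk group.

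**Misclassification.** The question covers any cardiovascular condition and identifies no drug class. By the plan's own source, most people with coronary calcium are already on some cardiovascular treatment. For such a person, adding a lipid-lowering drug has no clear answer to a question about having initiated treatment, although it is the kind of change that a calcium report might prompt. A switch between two drugs of the same class is equally unclear. This arises even when every answer is honest.

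An analysis plan cannot repair either problem. If the year-1 medication list is not collected, drug class and new starts cannot be derived later.

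**Working it through.** **Inputs from Section 5.3 (ii).** Treated share among those with coronary calcium: 68% (non-reporting) and 73% (reporting). Share with calcium: 44%. Participants: 2,500 per arm. Test: chi-square, two-sided 5%.

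**Expected effect over all randomised participants.** (73% − 68%) × 44% = 2.2 points, and 0.022 × 2,500 = 55 participants per arm. The matching rates are 68% × 44% = 29.92% and 73% × 44% = 32.12%.

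**Formula.** For reported rates a and b with n per arm, let d = b − a, p̄ = (a + b)/2, s0 = √(2p̄(1 − p̄)/n) and s1 = √(a(1 − a)/n + b(1 − b)/n). The rejection probability is Φ((d − 1.96·s0)/s1) + Φ((−d − 1.96·s0)/s1).

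**The plan's own figure.** With a = 0.68, b = 0.73 and n = 2,500 the result is 97.25%, so the stated 97% reproduces, but only if the 44% is left out. At 29.92% against 32.12% the power is 39.0%. That is a separate point about the power statement. It matters here because it shows how small the target is: 2.2 points, with s0 about 1.3 points.

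**Assumed spurious difference with no true effect.** The base is the plan's 29.92%. The last row gives, for a 1-point shift, an assumed range of lower initiation rates.

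| Base rate | Spurious difference | Probability of p<0.05 |
|---|---|---|
| 29.92% | 0 | 5% |
| 29.92% | 0.5 points | 6.7% |
| 29.92% | 1 point | 12.0% |
| 29.92% | 1.5 points | 21.0% |
| 29.92% | 2.2 points | 39.0% |
| 5% / 10% / 20% | 1 point | 34% / 21% / 14% |

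Worked line for 1 point at 29.92%: s0 ≈ s1 ≈ 0.01301, so (0.01 − 1.96 × 0.01301)/0.01301 ≈ −1.19. Φ(−1.19) ≈ 0.117, and the other tail adds 0.003, giving 0.120.

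The lower bases are shown because 29.92% is a share on treatment, while the endpoint is initiation. The document gives no initiation rate.

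**What a 2.2-point shift would require at the 29.92% base.** Either a gap between arms in the sensitivity of self-report of 2.2/29.92 = 7.4 percentage points, or false positive answers from 2.2/(100 − 29.92) = 3.1% of untreated reporting-group participants. With a base of 68% the second figure is 2.2/32 = 6.9%. The document does not say whether differences of this size are likely.

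**The case against.** **The source may be better than the question suggests.** The line recording current medication stands under the consequences-of-screening sub-heading, and round 2 refers back to that sub-heading with an as-above reference. The evaluation text says that initiation, lipid-lowering in particular, will be determined, which implies some drug-class information. The exact questions are left to a stand-alone questionnaire that is not shown. This stands in part: a year-1 list may be intended. But the as-above reference is to the consequences-of-screening questionnaire, and no text says that medication is recorded again.

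**The two visits use parallel wording.** The baseline cardiovascular item is also a question. This is true. The difference is that baseline also has a staff assessment and a medication record.

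**Unrelated starts are balanced by randomisation.** This stands. Starts prompted by blood pressure or other reasons add noise, not bias. The question also fits the broad part of the endpoint; what it lacks is the drug class.

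**The outcome is exploratory.** This stands and limits formal error-rate claims. It does not remove bias, and Section 5.3 still powers the comparison and concludes that the study can evaluate potential cardiovascular benefit.

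**Stronger readings.** A reader might infer that the reporting bias is as large as the expected effect. The protocol gives no self-report accuracy in either arm, so a 2.2-point bias is a scenario only. Nor is this the only randomised comparison measured within the trial: smoking cessation is also compared between the randomised reporting groups.

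**Conclusion.** The point holds as a weakness in how the outcome is ascertained, not as a demonstrated bias. As written, the main secondary objective, which is exploratory under Section 5.2.2, depends at year 1 on an undifferentiated question put to participants who know their allocation, with no clear repeat of the medication record. The comparison is therefore open to differential self-report and to misclassification of those already treated.

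The size is unknown from the document. The 12% and 39% figures assume no true effect, 2,500 per arm, the 29.92% base and a spurious shift of 1 or 2.2 points. That base follows the plan in counting treatment only among those with calcium. The figures are higher if initiation is rarer. They show that the target is small enough for modest reporting differences to matter, and that a better source is available cheaply at a visit that already takes place. The change should be made, but the trial's primary comparison does not depend on it.

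**What to change.** In Section 6.1.2, second screening round, state that staff record the full current medication list at the year-1 visit in the same way as at baseline. Then:

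- Define initiation as a cardiovascular drug class on the year-1 list that is absent from the baseline list.
- Keep the endpoint as any cardiovascular treatment and report lipid-lowering drugs separately. Narrowing the endpoint to lipid-lowering drugs alone would change what is estimated and is not needed.
- Classify new starts blind to allocation.
- Keep the participant question as supportive information.

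The cost is one repeated eCRF page, a few minutes per visit and drug-class coding. A list based on what participants bring or report reduces reporting bias but does not fully remove it. GP contact details are already recorded and could support a check against practice records.
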